**Participants.** Veterans ( $n \approx 48$ , potential range 24-60) will be recruited from medical (e.g., primary care) and mental health programs throughout the facility and from the community. Given the feasibility aim of this project, ability to participate is intentionally broad to demonstrate demand and maintain ecological validity. Thus, inclusionary criteria are as follows: (1) self-identified as a BIPOC, (2) Veteran, (3) age 18 or older, (4) able to consent to study activities, and (5) endorsing one or more perceived discrimination experiences on the *Everyday Discrimination Form* (short version) or the *Major Experiences of Discrimination Scale* (abbreviated version; Sternthal, Slopen & Williams, 2011) "a few times a year" or more frequently and endorsing stress on a validated single-item measure (Elo, Leppanen, & Jahkola, 2003). Exclusionary criteria include: (1) serious mental illness, alcohol/substance use disorders, or cognitive impairment that may interfere with the ability to benefit from group (e.g., severe depression, psychotic illness, mania, dementia, **untreated** alcohol/substance dependence); and (2) serious suicidality or homicidality (e.g., ideation with plan/intent) that is likely to require urgent/emergent intervention within the study period.

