**Allostatic load** will be assessed pre and post intervention by measuring 10 markers of interest, specifically hemoglobin (Hb) A1c, systolic and diastolic blood pressure (SBP, DBP), high density lipoprotein (HDL), triglycerides, urine epinephrine (Epi) and norepinephrine (NE), waking salivary cortisol, interleukin (IL)-6, and hsCRP. **Venous blood will be drawn via vena puncture between 8-10 AM after overnight fasting and sent to the VA clinical chemistry lab to measure Hb A1c and the lipid panel (for HDL and triglycerides). Plasma from 5mL of blood will be collected and frozen at -80 C until assayed to measure IL-6 and hsCRP using electrochemiluminescence assay (Mesoscale Discovery). Spot urine will be collected for Epi and NE and frozen at -80 C until assayed using ELISA-based immunoassay and adjusted for creatinine levels, which are well representative of general sympathetic output of an individual. Salivary cortisol levels will be measured in saliva collected the morning of the blood draw visit upon wakening. Saliva samples will be frozen at -80 C until assayed using immunoassay (Salimetrics). Both pre and post samples from a given participant will be assayed together using reagents from a single lot number by one technician who is blinded to the condition. All biomarker assays will be done in [name] lab where they are routinely performed, and the intra- and inter-assay CV's of these proposed markers are <10%. Seated SBP and DBP will be measured after a 5-min of rest, and the average from 3 readings will be used. The AL index for each participant will be calculated by assigning 1 to the highest quartile values vs. the rest 0 for each marker and summing them (Rosemberg, Granner, Li & Seng, 2020).** Thus, a possible range of 0 to 10 would emerge, indicating the lowest to highest AL across the participants. We acknowledge that there have been differing ways for AL index calculation as well as included markers. Our proposed methods and the markers are based on the best consensus from a number of studies and reviews that also demonstrated evidence of AL reflecting chronic stress and eventual health outcomes including all-cause mortality (Duong et al., 2017; Guidi, Lucente, Sonino, & Fava, 2021; Juster, McEwen & Lupien, 2010).

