**Sample size.** As a feasibility study, the decision about sample size is not about establishing sufficient power to detect change in clinical outcomes but rather about demonstrating the viability of a future larger-scale study. The sample size was determined based on practical and quantitative considerations. We will aim for enrollment of 4 groups of each type of intervention, each with approximately 6 Veterans (average 6, range 4-10), leading to a total sample size of approximately 48 (24/cell) in the 15-month recruitment period. This rate of enrollment would demonstrate feasibility of a larger future study in that we would demonstrate that a steady flow of adequately sized intervention groups can be recruited. Given that this is a pilot and feasibility study, we are looking for clinical signal and feasibility rather than examining efficacy. All sample size analyses were performed using statistical package R. A two-sided type I error of 0.05 was assumed.

The sample size assessment was conducted for assessing the enrollment and completion rates. First, we assessed the precision of estimates based on projected sample size. We considered a range of target rate from 0.60 to 0.90 and estimated the width of the 95% exact binomial confidence interval for enrollment and completion rates for overall and for each intervention group (see **Table 1**).

**Table 1.** The width of 95% confidence intervals for enrollment and completion rates

Sample size	Estimated rate						
	0.60	0.65	0.70	0.75	0.80	0.85	0.90
48	0.267	0.261	0.251	0.239	0.222	0.201	0.174
24	0.365	0.357	0.345	0.329	0.308	0.282	0.249

From **Table 1**, if an estimated intervention initiation rate is 0.80, a sample size of 48 (total) and 24 (per intervention group) will produce a two-sided 95% confidence interval with a width of 0.222 and 0.308,

respectively. If an estimated intervention initiation rate is 0.90, the width of the 95% CI is reduced (becomes more precise, see **Table 1**) with the same sample size projected above.

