**Analyses.** The study has the goals of evaluating the viability and methodology of an RCT comparing two approaches to addressing race-based stress and trauma in VOC. Kraemer and colleagues (2006) have highlighted important limitations of effect sizes generated by pilot studies due to the large standard error. As a result, we will focus our analyses on examining feasibility and generating hypotheses for further examination. Descriptive statistics will be used to summarize the variables as well as to detect outliers, manage missing data and identify data entry errors. Wilcoxon rank sum test and Fisher's exact test will be used to assess the effectiveness of the randomization procedures by comparing baseline variables for participants between two intervention conditions. The primary analysis will be conducted for overall, and for each intervention group, respectively. The comparison of outcomes between intervention groups will be performed when it is necessary and appropriate. Multivariable analysis (logistic regression and linear regression) will be performed when it is appropriate. The associations between patient characteristics and other clinically important baseline variables with the study outcomes will also be assessed using univariate tests. Variables that are significantly associated with the study outcome (assessed by univariate test) or significantly different between study groups with  $p < 0.15$  will be included as potential covariates in the multivariable model. Backward elimination will be used to select the variables, and variables with  $p < 0.10$  will be retained in the final model. For the linear regression model, the outcome variable will be transformed if normal assumption of residuals is not satisfied.

**Aim 1:** *To examine the feasibility of recruiting VOC for an RCT comparing RBSTE and Present Centered Therapy (PCT) for management of stress related to discrimination experiences.*

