We will assess four outcome measures for enrollment and retention: 1) *enrollment rate* defined as the proportion of consented subjects among all screened and eligible patients; 2) *initiation rate* defined as the proportion of subjects who initiate the intervention among all consented subjects; 3) *per protocol completion rate* defined as the proportion of subjects who complete 5 or 6 sessions of intervention among those who start the intervention; 4) *intent-to-treat completion rate* defined as the proportion of subjects who complete 5 or 6 sessions of intervention among all randomized subjects. The 95% CI (based on normal approximation or exact binomial test when appropriate) will be estimated for all these rates for overall and by each intervention group. The rates for the RBSTE and PCT groups will be compared by Fisher's exact test. Multivariable analysis will be also performed to examine the difference in outcomes between intervention groups using logistic regression.

**Aim 2:** *To understand Veterans' views of the acceptability and appropriateness of treatment content, the feasibility of participation, and perceptions of provider behavior and attitudes.*

The AIM, IAM, FIM and Provider Rating Scales will be estimated by mean, SD and 95% CI. Intervention groups will be compared by Wilcoxon rank sum test. Multivariable analysis will be also performed to examine the difference in outcomes between intervention groups using linear regression.

**Aim 3:** *To optimize the strategy for holistic evaluation of intervention effects.*

As aforementioned, we will include a comprehensive list of cardiometabolic, neuroendocrine, and inflammatory markers that had been shown as reliable markers of AL in the literature to derive an AL index for each participant. We hypothesize that AL index at baseline will be associated with perceived discrimination as well as other psychosocial outcomes and that pre to post-intervention changes of AL index will differ between the two groups. We will perform regression analysis and variable selection using LASSO (Tibshirani 1996) to identify a smaller subset of the AL markers at baseline that show significant associations with psychosocial outcome measures. The effect size for pre and post change in AL markers will be estimated. This will inform future efficacy and effectiveness studies in potential reduction of a list of biomarkers to enhance feasibility, efficiency and reduce participant burden.

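### Aim 3 labels LASSO-selected biomarkers as significant, with no valid test behind the label and no check that the selection is stable

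*Combined protocol and SAP*

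**What the plan says.** In the combined protocol and SAP, the Allostatic load paragraph under Research Design and Methods defines the index "by measuring 10 markers of interest". The Sample size paragraph aims for groups averaging six Veterans, "leading to a total sample size of approximately 48 (24/cell) in the 15-month recruitment period"; the Participants paragraph gives a "potential range 24-60".

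Under Analyses, Aim 3, the plan states: "We will perform regression analysis and variable selection using LASSO". The purpose is to find a smaller subset of baseline markers "that show significant associations with psychosocial outcome measures". Pre-post effect sizes for the markers are also to be estimated. The plan then says: "This will inform future efficacy and effectiveness studies in potential reduction of a list of biomarkers".

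The opening of the Analyses section sets the general tone: because pilot effect sizes have large standard errors, "we will focus our analyses on examining feasibility and generating hypotheses for further examination".

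The text does not give a penalty rule, the psychosocial outcomes that enter this step, a definition of *significant* here, a method of inference after selection, or any resampling or validation. The general Analyses text has thresholds of 0.15 and 0.10 for choosing covariates, and the sample-size text assumes two-sided 0.05. Aim 3 refers to none of these.

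**The concern.** LASSO keeps a marker when its penalised coefficient is not zero. That depends on the penalty and carries no error rate. If significance is instead read from an ordinary regression on the selected markers, the same data have chosen and tested them, and the p-values are too small.

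The size of the data adds a second problem. With ten correlated candidates and about 48 people, the selected set can change a good deal between samples and between penalty rules, and the plan would not show this. Repeating the step over several scales adds chances for a false selection.

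Refining the assessment strategy is one of the study's three stated aims. A reader designing the next trial could take a list labelled significant as firmer than it is, and so keep noise markers or lose useful ones.

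**Working it through.** **Plan's own figures.** None covers the LASSO step. The nearest are the detectable effects at 80% power and two-sided 0.05: 0.60 (paired, n=24), 0.41 (paired, n=48) and 0.83 (24 per group). The t-test gives 0.597, 0.413 and 0.826, so they reproduce, but they concern mean changes and not marker selection.

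**Inputs from the documents.** N about 48 (range 24-60); ten markers; LASSO; several psychosocial outcomes.

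**Assumptions, because the documents give no values.** Zero or three true markers with equal coefficients; joint R² 0.1 to 0.5; pairwise marker correlation 0 to 0.5; penalty by 10-fold cross-validation under either the minimum-error rule or the one-standard-error (1-SE) rule.

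**1. Single-marker sensitivity (Fisher z).** The correlation detectable with 80% power at N=48 is tanh[(1.960 + 0.842)/√45] = tanh(0.418) = 0.40. With Bonferroni for ten markers it is tanh[(2.807 + 0.842)/√45] = 0.50. Power at r=0.3 is Φ(0.3095 × √45 − 1.960) = 55%.

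**2. No true association, N=48.** Under the minimum-error rule at least one marker is selected in 35-45% of trials across the batches run (correlations 0 to 0.5). Refitting the selected markers by ordinary regression gives at least one p<0.05 in 27% of trials (correlation 0.3, 400 trials) and about 36% (correlation 0.2). In the first of these, a selected null marker has p<0.05 in 34% of cases, not 5%. For comparison, ten unadjusted independent tests would give 1 − 0.95^10 = 40%. So the LASSO step does not create more false claims per trial than unadjusted testing; the fault is that the refitted p-values look like valid 5% tests. Under the 1-SE rule (correlation 0.2) a null marker is selected in only about 2-2.5% of trials.

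**3. Three true markers, N=48.** Exact-set recovery over correlations 0, 0.3 and 0.5 (400 trials per scenario):

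| Joint R² | Minimum-error | 1-SE |
|---|---|---|
| 0.1 | 1-2% | 0-0.5% |
| 0.2 | 1-4% | 0.5-2% |
| 0.3 | 4-7% | 5-13% |
| 0.5 | 6-7% | 18-37% |

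At R² 0.2 and correlation 0.3, the minimum-error rule keeps 1.9 of the three true markers plus 2.2 false ones, and two trials agree on the set 0.5% of the time. The 1-SE rule selects nothing in 60% of trials. At R² 0.2, even the best penalty on the path, chosen with knowledge of the truth, gives the exact set in only 7-16% of trials.

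**4. A stronger signal.** Three coefficients of 0.3 at correlation 0.2 give signal variance 3(0.09) + 6(0.09)(0.2) = 0.378. That is R² 0.38 if the outcome has variance 1, or 0.378/1.378 = 0.27 if the residual has variance 1. Exact recovery in this setting was 7-11% (minimum-error) and 18-21% (1-SE). Each unrelated marker was kept in 39-42% and 9% of trials, and each true marker in 91-93% and 62%.

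**5. Range of N.** At correlation 0.3 and R² 0.2 to 0.3, exact recovery is 1-2.5% at N=24 and 3.5-12% at N=60, over both rules.

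**6. Several outcomes.** The Holistic evaluation text lists six self-report instruments. If all six were used and were independent, the chance of at least one false selection would be 1 − 0.63^6 = 94% at 37% per outcome (minimum-error), or 1 − 0.975^6 = 14% at 2.5% (1-SE). Positively correlated scales would give less.

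**The case against.** A reader might infer that one LASSO fit will fix the panel for the next trial, as if the subset were established. The documents do not support that. The step is to serve "in potential reduction of a list of biomarkers to enhance feasibility, efficiency and reduce participant burden", with the reduction described only as potential. The analyses are declared hypothesis-generating, the sample was expressly not sized for hypothesis testing, and no marker is dropped in this trial. Pre-post effect sizes also feed the decision. Nor does the text say there will be only one fit; it is merely silent on resampling and validation.

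It is also fair that the false-selection rates depend on a tuning rule the plan does not name: under the 1-SE rule, null selection falls to about 2-2.5%. Exact recovery is a severe standard for a screening step, since under the minimum-error rule in the stronger setting true markers are kept more than 90% of the time. No participant, feasibility target or between-arm conclusion is affected.

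All of this stands, and it limits the point. It does not rescue the word *significant*, which LASSO cannot supply. The strong dependence on an unnamed penalty rule is itself a reason to name the rule.

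**Conclusion.** The point holds as one of labelling and missing stability information. As worded, Aim 3 attaches significance to markers chosen by a method that does not test it. If ordinary p-values are used after minimum-error selection, roughly 27-36% of trials with no true association would report at least one significant marker.

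The selected set is also unstable. With three true markers, exact recovery is about 13% or less for joint R² up to 0.3 under both rules, and about 7-21% near R² 0.38. It would be too strong to say that LASSO cannot find the set at this size: at R² 0.5 with the 1-SE rule recovery reaches 18-37%, though that is still a minority of trials. All these figures rest on assumed signal strength, number of true markers and correlations, and on batches of a few hundred simulated trials or fewer. The invalidity of ordinary post-selection p-values does not depend on those assumptions.

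**What to change.** In Analyses, Aim 3:

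- Replace the wording on significant associations with: selected by LASSO (exploratory). Report no ordinary p-values for selected markers.
- Pre-specify the psychosocial outcomes and the penalty rule.
- For each outcome, report every marker's selection frequency from half-sample subsampling without replacement, or from a bootstrap with the penalty fixed from the original data, together with the cross-validated R². Avoid re-tuning cross-validation inside ordinary bootstrap samples. Copies of one person can then fall in different folds, and in a small check (25 datasets, 40 bootstraps each, R² 0.38) unrelated markers were selected 54% of the time on average.
- Present these beside the pre-post effect sizes already planned, with confidence intervals.
- State that no marker is dropped on the basis of this pilot alone.

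The last item is needed because resampling shows the instability without curing it. Half-sample stability selection (first three markers to enter, threshold 0.75, correlation 0.3) cut false markers from 2.2 to 0.14 at R² 0.2. It kept only 0.58 of the three true markers there, and 1.4 at R² 0.5. With no true marker it still kept at least one in 21% of trials. A low frequency at this sample size therefore does not show that a marker is useless.

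The cost is SAP wording and a little programming, with no new data. The downside is a less definite shortened list.
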